#### 4.1.4 Other EHR-Derived Outcomes

*Cross-reference: UNC IRBIS Application section A.9.1 (identifiers).*

Other measures collected through the PCORnet CDM include:

- Demographic information (birth date, sex, race, and ethnicity)
- Patient height and weight
- Health care provider information
- Death information (death date and source)
- Health care visit information (visit dates, primary payer, facility type, and provider ID)
- Diagnosis and condition information (condition data and type, diagnosis dates, and associated ICD/CPT codes) for:
  - Mental health disorders, defined by ICD-10 codes (e.g., depression, anxiety, schizophrenia, bipolar disorder, suicide attempt/intent)

- Number and type of CNCP conditions per ICD-10 codes (e.g., back pain, neck pain, headache, arthritis, HIV)
- Alcohol/substance misuse or abuse as measured by ICD-10 codes.
- Overall comorbidity using the Charlson Comorbidity Index per ICD-10 codes
- Opioid prescription information including RxNorm CUI (drug prescribed), prescription dates, dose, units, frequency, route, quantity, refills, and supply days.

We will calculate time to discontinuation of opioids, where discontinuation will be measured based on our previous work, except that the discontinuation will be defined as the first day of a minimum 90-day period with no opioid prescriptions (see Section 5.2 for additional information about the definitions and analyses).

A Schedule of Assessments indicating the timing and source of efficacy, safety, and fidelity measures is presented in **Table 6**.

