**Table 11. Reportable Events and Assessment Methods**

Reportable Event	Assessment Method
Suicide risk (active suicidal ideation or attempted suicide) (see section 8.3.5 below)	Adverse Event Case Report Form
All Deaths (including opioid-related, suicide, and all other deaths)	Adverse Event Case Report Form, PCORnet EHR-based data, National Death Index (available after study completion), publicly available data
Hospitalizations or Emergency Department (ED) visits related to opioid use (overdose or withdrawal) or related to suicide attempt	Adverse Event Case Report Form, PCORnet EHR-based data, patient self-report via 6- and 12-month follow-up surveys

When one of these AEs is identified, the institution PI or designee will assess the event to evaluate whether it is one of the following:

- Unanticipated (i.e., unexpected). These events are AEs that are new or greater than previously known, in terms of nature, severity, frequency or occurrence, as documented in the protocol, consent, or other study documents approved by the IRB (OHRP-  
<https://www.hhs.gov/ohrp/regulations-and-policy/guidance/reviewing-unanticipated-problems/index.html>).
- Related (possibly related, probably related, or definitely related) to study participation.

Institutions will record all reportable events in REDCap in the Adverse Event Case Report Form.

Reporting will either follow an expedited or periodic timeline.

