08/09/2021	13.0	
 • Revised to respond to IRB stipulations • Corrected minor errors
10/07/2021	14.0	
 • Corrected version numbers and dates in the list of attachments.
12/23/2021	15.0	
Revised to include publicly available data as a data source.
 
 •
3/30/2022	16.0	
 • Revised to describe procedures related to requesting death certificates: maintaining the confidentiality of the data, procedures for ensuring the privacy of subjects, and how these data will be used.

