6. SAMPLE SIZE DETERMINATION

Sample size estimates were generated to provide robust power to detect minimal clinically important differences (MCID) in reduction of opioid use between the 2 study arms.

A total sample size of 506 participants (253 per study arm) will provide 80% power to detect an effect size of a difference of 10 MED between the SDM and MI+CBT intervention arm using an analysis of covariance model with $\alpha=0.05$ and assuming a baseline model-adjusted standard deviation for change from baseline of 40 MED. The sample size was inflated by 20% (608 total participants; 304 per study arm) to account for potential variance inflation associated with CBT group delivery (based on a group

size of 8 and an interclass correlation coefficient of 0.01) and a potential loss of follow-up opioid prescription data on as many as 12% of participants.

For the PROMIS secondary outcome measures, the minimally important difference (MID) for the physical function scale is 2 units, whereas the MID for the pain interference scale is 3.5 units. For both instruments, we assume the standard deviation for change from baseline is 10 (see section 9.2 for a more thorough description of these secondary measures). With the planned total of 608 randomized participants and assuming 20% of those have missing PROMIS scale responses, the power for the PROMIS Pain Interference score is 96%, while the power for the PROMIS Physical Functioning scale is 57% (Table 6.1).

Note that the enrollment was slower than planned, and due to timeline constraints was stopped prior to reaching 608 randomized participants. Final study enrollment was 526 randomized participants. As of June 2023 (DSMB report), study discontinuation was at 20%;, but survey completion rate was tracking around 60% (40% missing, higher than the planned levels). Approximate post-hoc power based on the final sample size is provided in Table 6.1.

Table 6.1. Power for Primary and Key Secondary Outcomes

Total sample size	Primary aim: Power for opioid MED ¹	Secondary aim: power for PROMIS Pain Interference ²	Secondary aim: Power for PROMIS Physical Functioning ²
Planned 608	80%	96%	57%
Approximate post hoc power based on randomized (n=526)	75% based on protocol- assumed level of missing opioid prescription data	85% Based on number of completed surveys	40% Based on number of completed surveys

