Intent to Taper	Ordinal and Binary	
A question on the T1, T2, and T3 survey includes:
 
Please say how much you agree with this statement: "Reducing the amount of opioid medicines I take is a goal of mine" with response options including Strongly Agree, Agree, Uncertain, Disagree, and Strongly Disagree.
 
In addition to reporting the frequency of initial response options, responses of Strongly Agree and Agree will be re-classified as an intent to taper, while Uncertain, Disagree, and Strongly Disagree will be re-classified as no intent to taper.

Relative opioid use self-report (from T3 survey)	Ordinal	A question on the T2, and T3 survey includes my overall use of opioids has increased, stayed the same, decreased.
Safety Outcomes		
Adverse Events (AEs); 1) Opioid Withdrawal Overdose, 2) Suicidality Risk, and 3) Death	Count and proportion	Three different types of AEs will be collected throughout the intervention phase of the study (from randomization to 12-months post-randomization): 1) opioid withdrawal or overdose, 2) suicidality risk, and 3) death. AEs will be identified and reported from the REDCap study database, the 6 and 12-month follow-up surveys, and deaths from the electronic medical records (based on ICD-10 codes). To identify duplicate AE reporting and corroborate AE details, we collect AE type and onset date in each database. If the same AE is reported in multiple different databases, it will only be counted as one AE. The total number of AEs as well as any documented AE will be examined.
Subgroups and Other Covariates		

Variable	Type	Definition
Mental Health Disorder Flag(s)	Binary	
Includes an indicator for any mental health disorder recorded as a diagnosis in the EHR, as well as binary indicators for the presence in the EHR of each of the following: adjustment disorder, anxiety, ADHD, dementia, developmental disorder, childhood disorders, impulse control disorder, mood disorder, personality disorder, schizophrenia or other psychotic disorder, suicidal ideation, and other miscellaneous mental health disorders.
 
The ICD-10 codes used to identify Mental Health Disorders was pulled from the Healthcare Cost and Utilization Project Agency for Healthcare Research and Quality (H-CUP-AHRQ) website (https://hcup-us.ahrq.gov/toolssoftware/ccs10/ccs10.jsp#download)

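### SAP 9.2 finds EHR deaths by ICD-10 codes and does not name the CDM death field, the National Death Index or public records, so deaths outside the health system that sites do not learn of would be missed

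*SAP*

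**What the plan says.** Protocol Table 11 makes all deaths reportable and lists four ways of finding them: "Adverse Event Case Report Form, PCORnet EHR-based data, National Death Index (available after study completion), publicly available data". Protocol 4.1.4 lists the items drawn from the PCORnet CDM. One of them is "Death information (death date and source"), on a line separate from the diagnosis and condition codes. SAP 4.7 has its own Death row, marked under the CDM extraction.

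SAP 9.2 gives the analysis definition. It covers events "throughout the intervention phase of the study (from randomization to 12-months post-randomization"). For sources it says "AEs will be identified and reported from the REDCap study database, the 6 and 12-month follow-up surveys". The only EHR source it then gives for this outcome is worded "and deaths from the electronic medical records (based on ICD-10 codes"). The same entry counts an event reported in several databases once, matching on event type and onset date. SAP 9.7 compares the risk of each event type by arm and adds no further source.

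The SAP's protocol history repeats the version 15 change: "Revised to include publicly available data as a data source". The SAP definitions and safety analysis sections do not mention that source again, and the SAP text does not mention the National Death Index at all.

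**The concern.** Each source named in SAP 9.2 has a gap for the same kind of death.

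- A diagnosis code needs a recorded encounter or diagnosis. A death at home, or in another health system, may leave none.
- A participant who has died cannot answer a survey.
- Under Protocol 8.3.6 the adverse event form is completed when site staff become aware of the death.
- Under SAP 4.6, EHR and survey collection stops for participants found ineligible, for those who withdraw from all activities, and for some others.

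The sources that SAP 9.2 leaves unnamed are better suited to such deaths. The CDM death field does not have to rest on a diagnosis code. The National Death Index and public records do not require contact with the clinic.

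Death is the most serious of the three safety outcomes. A count that depends on what the clinics see is less complete for participants who have left their care.

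**Working it through.** **1. Sources side by side**

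| Source of deaths | Protocol | SAP |
|---|---|---|
| Adverse event form in REDCap | Table 11, 8.3.6 | Named in 9.2 |
| EHR data | Table 11 (PCORnet EHR-based data) | Named in 9.2, by ICD-10 codes |
| CDM death date and source | 4.1.4 | Death row in 4.7; not named in 9.2 |
| National Death Index | Table 11 | Not named |
| Publicly available data | Table 11 | Only in the protocol history in section 1 |
| 6- and 12-month surveys | Not listed for deaths | Named in 9.2 for adverse events generally |

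Two of the four Table 11 sources are absent from the analysis definition, and the EHR source is tied to diagnosis codes instead of the death field. The SAP explains other departures from the protocol: the time intervals (9.2 and 9.3), the random subject effect (9.3) and the time-to-discontinuation endpoint (9.6.3). It gives no reason for this one.

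**2. Which deaths the written rule would miss**

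A death is missed only if three things hold together: it leaves no ICD-10 code at the site, site staff do not learn of it, and no listed survey picks it up. If the site does learn of it, by any route, Protocol 8.3.1 requires an entry on the REDCap form, and REDCap is a SAP source. The death-certificate procedure in Protocol 8.3.6 does not close the gap, because it supplies the cause of a death already known.

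**3. Scale**

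The plan states no figure for missed deaths and no death rate, so there is nothing to reproduce. The inputs are:

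- 526 randomized (SAP 6).
- "study discontinuation was at 20" per cent as of June 2023 (SAP 6).
- Assumption: yearly mortality of 1% to 3%.
- Assumption: half a year unobserved, on average, for each participant who discontinued.

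Participants who discontinued: 526 × 0.20 = 105.2, about 105.

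Deaths expected in all participants over the 12-month window: 526 × 0.01 = 5.3, to 526 × 0.03 = 15.8.

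Deaths in unobserved time among discontinuers: 105 × 0.5 × 0.01 = 0.5, to 105 × 0.5 × 0.03 = 1.6.

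For this group the last line is an upper bound at each assumed rate. It treats every discontinuer as out of sight, whereas stopping the study is not the same as leaving the health system. It does not cover retained participants whose out-of-hospital deaths leave no code. The documents give no basis for a number there.

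**4. Effect on the comparison**

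Two illustrations use about 263 per arm (526 / 2) and start near balance. Restoring two deaths to one arm turns 2 vs 3 into 2 vs 5 (Fisher's exact p = 0.45), and 8 vs 8 into 8 vs 10 (p = 0.81). The counts change visibly, but the comparison is uninformative before and after.

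**The case against.** The strongest reply is that this is a wording mismatch with little practical effect.

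- **Public records.** A reader might infer that the SAP has dropped them. The documents do not support that: a death a site finds in public data goes onto the REDCap form and so into the count. What can be said is that SAP 9.2 does not name the source.
- **The CDM field.** A reader might infer that it will not be used. That is not shown either. SAP 4.7 schedules a death extraction, and SAP 9.2 refers to a separate dataset specification file that is not among the documents. The field may be used in practice, but the definition as written says ICD-10 codes.
- **The death index.** A reader might take it for the only source independent of retention. Table 11 also lists public data, which does not require clinic attendance. Table 11 marks the index as available only after study completion, so its absence from an analysis of locked databases may reflect timing. Consent also limits it. Under Protocol 3.12, no more data are collected from participants who withdraw before any intervention, and later withdrawals need permission even for continued EHR extraction.
- **Follow-up after discontinuation.** SAP 4.6 plans to continue surveys and EHR extraction, with listed exceptions, so the 105 overstates the number unobserved.
- **Consequence.** SAP 7.6 makes every comparison beyond the primary and two key secondary outcomes descriptive.

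All of this stands as a limit on size. It does not remove the conflict: SAP 9.2 states a rule that differs from Table 11 and sits poorly with the SAP's own Death row, without explanation.

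**Conclusion.** The point holds as a conflict between a stated SAP rule and the sources the protocol lists. Applied literally, SAP 9.2 would undercount deaths that occur outside the health system and that sites do not learn of.

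The size cannot be derived from the documents. Under the two assumptions above, at most about 0.5 to 1.6 deaths among the roughly 105 discontinuers fall in unobserved time, and an unknown share of those would in fact be missed.

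A reader might go further and infer that the missed deaths would differ by arm or reverse a safety conclusion. The documents report no difference in retention between arms, and the illustrations show two restored deaths leaving the comparison inconclusive. What is at stake is the completeness of a descriptive table of the most serious safety outcome. No formal hypothesis test depends on it.

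**What to change.** In SAP 9.2:

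1. Define death as the union of the REDCap adverse event form, the CDM death date and source field, and publicly available data, using the de-duplication rule already there.
2. Do not rely on ICD-10 codes alone to identify deaths, and bring the wording into line with the Death row in SAP 4.7.
3. Add National Death Index results, where consent permits, as an update after lock. Otherwise state why the index is not used.
4. Report the number of deaths by source and by arm.

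The first, second and fourth changes cost SAP wording and the use of sources the protocol already lists. The third costs more: the protocol text gives no linkage procedure, consent has to be checked for participants who withdrew, and the death table may need a single update after lock.

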4.4 Electronic Health Record (HER) Data in the CDM

4.4.1 Data Stored in the CDM

The EHR data extracted from the CDM contains the study's primary outcome (average daily opioid dose in MED), which is derived from each participant's prescription data. This data source also contains important subgroup variables including vital signs and CNCP, and substance use and mental health diagnoses. The study will also be extracting potential adverse events based on ICD-10 codes and insurance provider information. Each site will also perform a separate 'sidecar' request to pull out the total number of SDM visits per participant (based on attendance at a healthcare visit with a trained SDM provider, clinic notes and smartphrases), including the delivery mode of the visit (in-person vs. telehealth). A sidecar request is necessary for this type of data since this data is not included in the CDM.

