8.3 Study Interventions and Adherence

Participants will be randomized (based on a 1:1 ratio) to receive either a SDM or MI+CBT intervention. SDM seeks to explore and compare treatment options, assess a patient's values and preferences, and reach a shared decision between a patient and provider regarding current pain management options. CBT is an empirically based behavioral pain management therapy intervention which has been found effective for chronic pain. MI will be used to enhance motivation for active participation in the CBT sessions. This arm includes 1 individual MI session and 8 CBT-CP weekly group therapy sessions. Throughout the study, participants in each of the study arms will receive guideline-concordant care (GCC), as based on CDC guidelines. The guidelines give guidance about medication selection, dose and duration, when and how to assess progress, and discontinue medication if needed.

The study will incorporate three separate Fidelity Case Report Forms (CRFs) to assess adherence for each study intervention. More information on intervention fidelity are included in a separate Fidelity Assessment Plan. The number of completed SDM visits and CBT group sessions will be reported. CBT session attendance is recorded by the study site in the REDCap database. The number of SDM visits are obtained by a sidecar data extraction from the EHR as described in Section 4.4.1.

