Substance Use Disorders Flag(s)	Binary	
Includes an indicator for any substance use disorder recorded as a diagnosis in the EHR, as well as binary indicators for the presence in the EHR of each of the following: alcohol use disorder and substance use disorder.
 
The ICD-10 codes used to identify Substance Use Disorders was pulled from the Healthcare Cost and Utilization Project Agency for Healthcare Research and Quality (H-CUP-AHRQ) website (https://hcup-us.ahrq.gov/toolssoftware/ccs10/ccs10.jsp#download)

Age	Continuous and categories	
As reported on the T1 (baseline) survey and captured in REDCap.
 
Age category will also be calculated as:
 
 < 50 50-64 >= 65
Intervention Delivery Mode	Categorical and Binary	
Due to the COVID-19 pandemic, the study began offering telehealth intervention visits beginning in early-May 2020. The intervention visit Case Report Forms (CRFs) were modified to document if a specific intervention visit was administered via telehealth or in-person visit. Since the CRFs were not modified until early-August 2020, all visits up-to-that point will be defined as in-person visits. Descriptive statistics of intervention delivery mode by intervention will be displayed (in-person only, telehealth only, and mixed mode); however, for adjusted analyses, mixed mode will be combined with telehealth to create a binary classification variable.

Variable	Type	Definition
Baseline Opioid MED categories	Ordinal	See the first row in this table regarding the derivation of average daily opioid prescription (in MED). Prescriptions provided 3-months, or 90-days prior to randomization will be considered a participant's baseline opioid MED, classified as None (0 MED), Very low (1-<20 MED) Low (20 - <50 MED), Moderate (50 - <90 MED), and High (90+ MED).
BMI	Continuous and categories	
Derived based on the participant's weight and height obtained from the EHR data (pulled within 90-days of the randomization date).
 
BMI category will also be calculated as:
 
 underweight: <18.5 normal 18.5 - < 25 Overweight 25 - < 30 Obese 30 - <40 Extremely obese >=40 
A dichotomous flag will also be calculated for BMI obese vs not obese.

Sex	Binary	As collected from the T1 (baseline survey); based on birth certificate.

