Number of Unique Chronic non-cancer pain (CNCP) Diagnoses	Count	
A count of the total number of unique CNCP diagnoses from the EHR data (diagnosis codes were pulled 3-months prior to the randomization date); a list of all CNCP diagnosis codes can be found in the specifications file.
 
The ICD-10 codes used to classify the different CNCP ICD-10 codes was pulled from the Healthcare Cost and Utilization Project Agency for Healthcare Research and Quality (H-CUP-AHRQ) website (Clinical Classifications Software Refined (CCSR) for ICD-10-CM Diagnoses (ahq.gov))

Site	Categorical	3 different study sites – Duke, UNC, and Vanderbilt; Site is captured in the REDCap database
Number of Completed MI and CBT Sessions	Count and categories	
The total number of completed MI and CBT sessions will be derived from the REDCap database. Per the protocol, there is 1 MI session and 8 different group CBT sessions.
 
Categories will be defined as: Number of intervention sessions received: MI/CBT: 0, 1-2, 3-4, >4)

Variable	Type	Definition
Number of Completed SDM visits	Count and categories	
The participant's total number of SDM visits will be derived from the SDM sidecar request from each study site. Note: in the SDM sidecar dataset received from study sites, each documented SDM visit from a trained SDM clinician is supplied with the associated SDM visit date and delivery mode (in-person or telehealth). Only SDM visits within the 12-month intervention phase will be counted in the total number of completed SDM visits.
 
Categories will be defined as: Number of intervention sessions received: SDM: (0, 1-2, 3-4, >4)

Incidence of other types of pain treatments used	Binary and count	These are reported as collected on the T1-T3 survey (no derivations required) and include: non-opioid medications, over the counter pain reliever, topical pain relievers, herbal pain reliever, cortisone injections, acupuncture, hypnosis, meditation, yoga, massage, psychotherapy, CBT, chiropractic treatment, relaxation training, physical therapy, hydrotherapy, ice or heat therapy, Transcutaneous Electrical Nerve Stimulation (TENS), and other.

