9.6.5 Exploratory Evaluation of Heterogeneity of Intervention Response to Opioid Use

We will explore treatment heterogeneity for a set of 10 potential covariates listed below, as specified in the protocol and defined in section 9.2 above:

- presence of substance use disorders (yes/no)
- presence of comorbid diseases (Charlson comorbidity index none vs 1 or more),
- Age (< 50, 50-64, 65+),
- baseline pain (BPI pain severity score of mild, moderate, severe),

- health literacy (high, average, and low),
- BMI categories (obese vs. not obese),
- Taking non-opioid pain medications prescribed (yes/no) per T1 survey
- Baseline opioid dose categories (very low, low, moderate, and high).
- Intervention delivery mode (in-person vs. telehealth),
- Number of intervention visits/sessions received: 0, 1-2, 3-4, >4

Testing for heterogeneity of intervention effects for these subgroups will be considered *exploratory*, and the results will be interpreted with appropriate caution. The outcome of interest for these analyses will be change from baseline to 12-months in average prescribed daily opioid dose (in MED). Analyses for these 10 covariates will be conducted the same as for the 2 specified subgroups above (Section 9.6.4), except that p-values will be interpreted descriptively only.

Each covariate will be added individually to a repeated measures MMRM models similar to the primary model described above while intervention arm is still adjusted for in the model .

9.6.6 Percent of Participants Who Experienced an Increase in Pain and Decrease in Opioid Dose

We will explore the percentage of participants per intervention arm who experienced an increase in pain and a decrease in opioid dose. For this analysis, we will create a binary variable for both the PROMIS Pain Interference and Physical Functioning outcomes that identifies participants that experienced an increase in these measures at 12-months since baseline (i.e.: an increase in the Pain Interference T-Score at 12-months and a decrease in the Physical Functioning T-Score at 12-months). We will then categorize their opioid use at 12-months in comparison to baseline as: unchanged (within +/- 10 MED), decreased (<10 MED), or increased (>10 MED).

We will provide descriptive statistics via contingency table that displays the count and proportion of participants, per intervention arm, that experienced an increase in pain but a decrease in opioid prescriptions. No hypothesis or statistical testing will occur.

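### SAP 9.2 codes telehealth MI/CBT sessions held between early May and early August 2020 as in-person, and does not say whether recorded SDM modes override that rule

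*SAP*

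**What the plan says.** The Intervention Delivery Mode entry in SAP 9.2 gives two dates. It says that "the study began offering telehealth intervention visits beginning in early-May 2020", and that the case report forms could record mode only from early August 2020. For the gap it sets a fixed value: "Since the CRFs were not modified until early-August 2020, all visits up-to-that point will be defined as in-person visits". The variable is shown descriptively in three levels (in-person only, telehealth only, mixed). For adjusted analyses, "mixed mode will be combined with telehealth to create a binary classification variable".

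The two arms draw on different sources. For SDM, SAP 4.4.1 and 9.2 use a separate sidecar request to each site, in which "each documented SDM visit from a trained SDM clinician is supplied with the associated SDM visit date and delivery mode". For the other arm, SAP 8.3 says "CBT session attendance is recorded by the study site in the REDCap database", and the SAP names no other source for MI/CBT mode. Protocol Table 5 shows that visit status is entered in REDCap for SDM as well.

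Delivery mode is one of the 10 covariates in SAP 9.6.5, analysed with the interaction model of 9.6.4 and with p-values read descriptively. Protocol 5.3.3 plans the same exploration.

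**The concern.** The mode of these sessions was not recorded, and the rule fills the gap with one fixed value. By the SAP's own dates, that value is wrong for every telehealth session in the window. The rule also does not say how it relates to the sidecar data. If it covers SDM visits, modes already known from the EHR are replaced. If it does not, the miscoding sits in one arm only. In that case some remotely treated MI/CBT participants join the in-person group while SDM participants are classified correctly, which can distort the arm-by-mode contrast in either direction.

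What is at stake is the descriptive table of mode by arm and one exploratory heterogeneity analysis.

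**Working it through.** The plan gives no figure here to reproduce. The check has three parts: the length of the window, which attendance patterns end up in the wrong class, and an illustration of scale.

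**1. Window against course length**
- 1 May to 1 August 2020: 31 + 30 + 31 = 92 days, or 92/7 = 13.1 weeks. Reading each 'early' as anywhere from the 1st to the 10th of the month gives 83 to 101 days.
- SAP 8.3 plans 8 weekly group sessions: 7 intervals × 7 days = 49 days from first to last.
- 92 − 49 = 43 days of possible start dates put a whole group course inside the window (34 to 52 days over the range above).
- Delivery ran from about April 2019 (Protocol 2.5) to March 2023 (SAP 4.6), about 1,460 days. The window is 92/1,460 = 6.3% of that.

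**2. Which MI/CBT patterns are misclassified**

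| True pattern | Three-level code under the rule | Binary code under the rule |
|---|---|---|
| All sessions before early May 2020 | in-person only: correct | in-person: correct |
| All sessions remote and inside the window | in-person only: wrong | in-person: wrong |
| In-person before, remote in window, none later | in-person only: wrong (truly mixed) | in-person: wrong |
| Remote in window, in-person later | in-person only: wrong (truly mixed) | in-person: wrong |
| Remote in window, remote later, none in person | mixed: wrong (truly telehealth only) | telehealth: correct |
| At least one in-person, remote in window, remote later | mixed: correct | telehealth: correct |

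The binary variable therefore fails only when a participant has a remote session in the window and no telehealth session recorded afterwards. The three-level table has one more failing pattern. If the rule is applied literally to all visits, the same logic extends to SDM participants.

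**3. Scale, as illustration only**

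Assume 526 randomized (SAP 6) split evenly, so 263 per arm. Assume uniform enrollment over April 2019 to March 2022 (1,095 days), CBT starting at enrollment, full weekly attendance and no pandemic pause. The start rate is 263/1,095 = 0.240 per day.
- Whole group course inside the window: 43 × 0.240 = about 10 participants (43/1,095 = 3.9%).
- Last group session inside the window: 92 × 0.240 = about 22 (8.4%). These have no later group session that could correct the binary variable.
- Any group session inside the window: (92 + 49) × 0.240 = about 34 (12.9%).

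These are numbers exposed to the window, not numbers miscoded. Miscoding also requires that sessions in the window were remote.

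**The case against.** The strongest reply is that this is a disclosed convention for a minor variable. Delivery mode is one of 10 exploratory covariates. It is not in the primary model (SAP 9.3) or in the analogous key secondary models (SAP 9.5.1). It is also a post-randomization variable tied to calendar time and the pandemic, so an arm-by-mode contrast would not be causal even if coded perfectly. Pooling mixed mode with telehealth already corrects the binary variable for anyone with a later recorded telehealth session. All of this stands. It limits the importance of the point but does not make the rule correct.

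A reader might also infer more than the documents support:
- *That every visit before August 2020 is miscoded.* By the SAP's own dates, visits before early May 2020 were in person.
- *That visits in the window were all or mostly remote.* The SAP says telehealth was offered, and Protocol 6 makes remote visits conditional on being appropriate and possible.
- *That the error is certainly confined to the MI/CBT arm.* The SAP does not state which source governs SDM mode.

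The illustration in the working can be challenged too. Remote enrollment entered the protocol only with version 11, dated 8 July 2020. Someone enrolled remotely after that who attended the weekly course would have sessions beyond early August and be captured by the revised form. Enrollment may also not have been uniform through the window. The counts therefore carry no evidential weight beyond showing that the number need not be zero.

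**Conclusion.** The point holds, and it is minor. The SAP's dates and its coding rule conflict for telehealth MI/CBT sessions held between early May and early August 2020, and a full weekly group course fits inside that window. The SAP also leaves open whether sidecar mode takes precedence for SDM visits, so the plan either overwrites known values or treats the arms unequally. The error reaches the binary variable only for participants with a remote session in the window and no later recorded telehealth session. It reaches the three-level table more widely.

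The number of participants affected is not in the documents. The conclusion rests on the SAP's dates being accurate and on at least some sessions in the window having been remote. The documents do not support a claim that the primary or key secondary results are biased, or that a spurious arm-by-mode interaction is likely.

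**What to change.** Amend the Intervention Delivery Mode entry in SAP 9.2 to say:
- The delivery mode in the sidecar extract governs all SDM visits.
- MI/CBT visits before early May 2020 are in-person.
- MI/CBT mode from early May to early August 2020 is unknown, unless it can be recovered from the EHR session notes described in Protocol 6.3.1 and 10.1.
- A participant is left out of the delivery-mode analysis only if the class depends on an unknown session. For the binary variable, that means at least one unknown session and no recorded telehealth session. The descriptive table gains an unknown category.
- A sensitivity analysis codes the unknown sessions as telehealth.

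The cost is a few sentences in the SAP and one extra run of an exploratory model. Some MI/CBT participants, probably few, would be lost from that analysis. They would be selected by calendar period and from one arm, which is why the sensitivity analysis is needed. Recovering mode from the EHR should not be assumed to be a small task: SDM mode itself needed a separate request at each site because it is not in the common data model, and the documents do not say that session notes record CBT mode in extractable form.
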